10.1.4 SAEs

An SAE is defined as any untoward medical occurrence that at any dose:

1. Results in DEATH.
2. Is LIFE THREATENING.
 - The term “life threatening” refers to an event in which the subject was at risk of death at the time of the event; it does not refer to an event that hypothetically might have caused death if it were more severe.
3. Requires inpatient HOSPITALIZATION or prolongation of existing hospitalization.
4. Results in persistent or significant DISABILITY/INCAPACITY.
5. Is a CONGENITAL ANOMALY/BIRTH DEFECT.
6. Is an IMPORTANT MEDICAL EVENT that satisfies any of the following:
 - May require intervention to prevent items 1 through 5 above.
 - May expose the subject to danger, even though the event is not immediately life threatening or fatal or does not result in hospitalization.
 - Includes any event or synonym described in the Takeda Medically Significant AE List ([Table 10.a](#)).

Table 10.a Takeda Medically Significant AE List

	Term
Acute respiratory failure/acute respiratory distress syndrome	Hepatic necrosis
Torsade de pointes / ventricular fibrillation / ventricular tachycardia	Acute liver failure Anaphylactic shock
Malignant hypertension	Acute renal failure
Convulsive seizure	Pulmonary hypertension
Agranulocytosis	Pulmonary fibrosis
Aplastic anemia	Confirmed or suspected endotoxin shock
Toxic epidermal necrolysis/Stevens-Johnson syndrome	Confirmed or suspected transmission of infectious agent by a medicinal product Neuroleptic malignant syndrome / malignant hyperthermia Spontaneous abortion / stillbirth and fetal death

Note: Terms identified on the Medically Significant AE List represent the broad medical concepts to be considered as “Important Medical Events” satisfying SAE reporting requirements.

Predose events that fulfill 1 or more of the serious criteria above are also to be considered SAEs and should be reported and followed up in the same manner (see Sections 10.2.2 and 10.3).

10.1.5 AEs of Special Interest

An AE of special interest (AESI), serious or non-serious, is one of scientific and medical concern specific to the compound or program, for which ongoing monitoring and rapid communication by the investigator to Takeda may be appropriate. Such events may require further investigation in order to characterize and understand them and would be described in protocols and instructions provided for investigators as to how and when they should be reported to Takeda. Pancreatitis, hypersensitivity, and hepatic events are considered AESIs and full details of the event should be recorded using the relevant AESI forms.

10.1.6 Intensity of AEs

The different categories of intensity (severity) are characterized as follows:

- Mild: The event is transient and easily tolerated by the subject.
- Moderate: The event causes the subject discomfort and interrupts the subject’s usual activities.
- Severe: The event causes considerable interference with the subject’s usual activities.

10.1.7 Relationship of AEs to Study Drug(s)

The relationship (causality) of each AE to study drug(s) will be assessed using the following categories:

- Related: An AE that follows a reasonable temporal sequence from administration of a drug (including the course after withdrawal of the drug), or for which possible involvement of the drug cannot be ruled out, although factors other than the drug, such as underlying diseases, complications, concomitant medications and concurrent treatments, may also be responsible.
- Not Related: An AE that does not follow a reasonable temporal sequence from administration of a drug and/or that can reasonably be explained by other factors, such as underlying diseases, complications, concomitant medications and concurrent treatments.

10.1.8 Relationship to Study Procedures

Relationship (causality) to study procedures should be determined for all AEs.

The relationship should be assessed as Related if the investigator considers that there is reasonable possibility that an event is due to a study procedure. Otherwise, the relationship should be assessed as Not Related.

10.1.9 Start Date

The start date of the AE is the date that the first signs/symptoms were noted by the subject and/or investigator.

10.1.10 Stop Date

The stop date of the AE is the date at which the subject recovered, the event resolved but with sequelae or the subject died.

10.1.11 Frequency

Episodic AEs (eg, vomiting) or those which occur repeatedly over a period of consecutive days are intermittent. All other events are continuous.

10.1.12 Action Concerning Study Drug

- Drug withdrawn – a study drug is stopped due to the particular AE.
- Dose not changed – the particular AE did not require stopping a study drug.
- Unknown – only to be used if it has not been possible to determine what action has been taken.
- Not Applicable – a study drug was stopped for a reason other than the particular AE eg, the study has been terminated, the subject died, dosing with study drug was already stopped before the onset of the AE.

10.1.13 Outcome

- Recovered/Resolved – Subject returned to first assessment status with respect to the AE.

- Recovering/resolving – the intensity is lowered by 1 or more stages: the diagnosis or signs/symptoms has almost disappeared; the abnormal laboratory value improved, but has not returned to the normal range or to Baseline; the subject died from a cause other than the particular AE with the condition remaining “recovering/resolving”.
- Not recovered/not resolved – there is no change in the diagnosis, signs or symptoms; the intensity of the diagnosis, signs/ symptoms or laboratory value on the last day of the observed study period has got worse than when it started; is an irreversible congenital anomaly; the subject died from another cause with the particular AE state remaining “Not recovered/not resolved”.
- Resolved with sequelae – the subject recovered from an acute AE but was left with permanent/significant impairment (eg, recovered from a cardiovascular accident but with some persisting paresis).
- Fatal – the AEs which are considered as the cause of death.
- Unknown – the course of the AE cannot be followed up due to hospital change or residence change at the end of the subject’s participation in the study.

10.2 Procedures

10.2.1 Collection and Reporting of AEs

10.2.1.1 AE Collection Period

Collection of AEs will commence from the time the subject signs the informed consent to participate in the study and continue until 14±2 days after Study Exit Visit or the last dose of study medication.

10.2.1.2 AE Reporting

At each study visit, the investigator will assess whether any subjective AEs have occurred. A neutral question, such as “How have you been feeling since your last visit?” may be asked. Subjects may report AEs occurring at any other time during the study.

All subjects experiencing AEs, whether considered associated with the use of the study drug or not, must be monitored until the symptoms subside and any clinically relevant changes in laboratory values have returned to Baseline or until there is a satisfactory explanation for the changes observed. All AEs will be documented in the AE page of the eCRF, whether or not the investigator concludes that the event is related to the study drug. The following information will be documented for each event:

1. Event term.
2. Start and stop date.
3. Frequency.

4. Intensity.
5. Investigator's opinion of the causal relationship between the event and administration of study drug(s) (related or not related).
6. Investigator's opinion of the causal relationship to study procedure(s), including the details of the suspected procedure.
7. Action concerning study drug.
8. Outcome of event.
9. Seriousness.

10.2.1.3 AEs of Special Interest

If an AESI, including but not limited to hypersensitivity, pancreatitis, hepatic disorders, occurs during the drug intake period or the follow-up period, is considered to be clinically significant based on the criteria below, it should be recorded in a targeted form or an SAE Form. The form should be completed and reported to the SAE email address within 24 hours.

AESI criteria include:

- Laboratory value threshold if applicable.
- Premature termination for the AESI, if applicable.
- Any other specific criteria.

The AESIs have to be recorded as AEs in the eCRF. An evaluation form along with all other required documentation must be submitted to the sponsor.

10.2.2 Collection and Reporting of SAEs

When an SAE occurs through the AE collection period it should be reported according to the following procedure:

A Takeda SAE form must be completed, in English, and signed by the investigator immediately or within 24 hours of first onset or notification of the event. The information should be completed as fully as possible but contain, at a minimum:

- A short description of the event and the reason why the event is categorized as serious.
- Subject identification number.
- Investigator's name.
- Name of the study drug(s).
- Causality assessment.

The SAE form should be transmitted within 24 hours to the attention of the contact listed in Section [1.0](#).

Any SAE spontaneously reported to the investigator following the AE collection period should be reported to the sponsor if considered related to study participation.

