13.1.4 Subject Condition Assessments

Subject condition assessments will be performed using the Safety Set. All subject condition assessments, including AEs, clinical laboratory evaluations, 12-lead ECG results, and vital signs will be summarized with descriptive statistics, where appropriate, and presented in the data listings.

All AEs will be coded using MedDRA and presented in the data listings.

A postdose AE is defined as an AE that occurs after the subject receives the first dose of study medication and within 30 days after the last dose of study medication is received. Summary of AEs will include numbers and percentages of subjects experiencing AEs by system organ class and preferred term. AEs will also be summarized based on their intensity and relationship to study medication by system organ class and preferred term. If a subject has more than 1 AE that codes to the same preferred term, the subject will be counted only once for that preferred term within regimen. Similarly, if a subject has more than 1 AE within a system organ class category, the subject will be counted only once in the system organ class category within the regimen. In the intensity summary, a subject will be counted only in the highest intensity category for each preferred term and each organ class. In the relationship to study medication summary, a subject will be counted only in the highest relationship category for each preferred term and each system organ class. Each summary table will include incidences of adverse events for each regimen and overall.

All AE summary tables will be listed in the SAP.

AEs will be summarized using preferred term and primary system organ class.

Individual results for clinical hematology and serum chemistry laboratory tests that are outside of normal range and results that meet Takeda predefined criteria for markedly abnormal values will be considered as clinically significant and identified in summary tables, if applicable. Observed values and change from Baseline will be summarized by regimen. All laboratory values will be presented in the data listings.

Individual vital sign values that meet the Takeda predefined markedly abnormal criteria will be considered as clinically significant and identified in a summary table. The vital sign measurements at predefined time points and change from Baseline will be summarized by regimen. All vital signs data will be presented in the data listing.

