Appendix A Schedule of Study Procedures

Study Day:	Days -28 to -2 (b)	Drug Intake Periods 1 through 4 (a)					Study Exit (Day 4 of Period 4)/ Early Termination Visit	Follow-up Phone Call (d)
		Day -1 (Check-in)	Day 1 (c)	Day 2	Day 3	Day 4 (Periods 1, 2, and 3)		
Informed consent	X							
Inclusion/exclusion criteria	X	X						
Demographics and medical history	X							
Medication history	X							
Physical examination	X	X					X	
Vital signs (e)	X	X	X			X	X	
Height, weight and BMI	X							
Concomitant medications	X	X	X	X	X	X	X	X
12-lead ECG (f)	X	X					X	
Clinical laboratory evaluations (g)	X		X (h)				X	
Urine drug, cotinine, and alcohol breath screen	X	X			X	X	X	
Urine pregnancy test (hCG) (i)	X	X					X	
HBsAg, Anti-HCV, HIV, and syphilis (i)	X							
Confinement		X	X (j)	X (j)				
Study drug dosing (k)			X					
PK blood collection (l)			X	X	X	X	X	
Predose/AE assessment (m)	X	X	X	X	X	X	X	X

Footnotes are on the following page.

CONFIDENTIAL

- (a) There will be at least 7 days between the dose in 1 period and the dose in a subsequent period.
- (b) Screening may consist of 1 or more visits. Subjects will sign an informed consent form at the first visit and return to the clinic in a fasted state for safety laboratory testing at the second visit. Screening procedures must be performed within 28 days prior to administration of investigational product.
- (c) Day 1 of each drug intake period.
- (d) Follow-up phone call will be made 14 ± 2 days after study exit to inquire about any AE or SAEs, and concomitant medications taken since final dose. Any AE/SAE spontaneously reported within 30 days postdose will be included within the database as AEs.
- (e) Vital signs: oral body temperature, sitting blood pressure (after resting 5 minutes), respiratory rate, and pulse (beats per minute). Vital signs will be measured just prior to dosing on Day 1 of periods 1 through 4. When vital signs are scheduled at the same time as blood draws, the blood draw will take priority and vital signs will be obtained within 0.5 hour before or after the scheduled blood draw.
- (f) ECG performed at Screening, Check-in (Day -1 of Period 1), and Study Exit Day 4 of Period 4, or if a subject terminates early from the study.
- (g) Hematology, serum chemistries, and urinalysis tests will be done at a local laboratory.
- (h) Predose hematology, serum chemistries, and urinalysis tests will be done for Period 1 only.

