- (i) A urine pregnancy test and HBsAg, Anti-HCV, HIV, and syphilis tests will be done locally.
- (j) Following the 24-hour blood sample collection on Day 2 of each period, subjects will be discharged from the clinic and will return to the clinic for the 36-hour blood sample collection on Day 2 and on Days 3 and 4 of each period to complete study procedures.
- (k) Study drug will be administered on Day 1 of each period at 08:00 (± 1) hours, following an 8- hour fast. Dosing may be staggered to help facilitate logistics at the site.
- (l) Blood samples for PK obtained predose (within 15 minutes prior to dose), 0.25, 0.5, 1, 1.5, 2, 3, 4, 6, 8, 12, 16, 24, 36, 48, and 72 hours postdose. The PK sample should not be collected at the Early Termination Visit if a PK collection is not scheduled.
- (m) Predose AEs will be captured immediately following the signing of the informed consent at Screening until dosing on Day 1 of Period 1. The routine collection of AEs will continue through to the follow-up phone call.

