7.11.1 Adverse Events

A treatment-emergent adverse event (TEAE) is defined as an adverse event (AE) or serious adverse event (SAE) that started or worsened after first study drug administration and within 14 days (30 days if SAE) of last dose of study drug (onset date – date of last dose + 1 ≤ 14), see Protocol Section 10.2.1.1. A TEAE will be attributed to a regimen if the TEAE occurs after administration of the study drug in a period and up to just prior to study drug administration in the next period. A TEAE that occurs after administration of the study drug in the last period and up to 14 days after the last study drug dose is attributed to the regimen received in the last period. All AE verbatim terms will be coded by system organ class (SOC) and preferred term using (PT) the MedDRA coding system. Any subject that doesn't not complete all 4 regimens/periods will be included in the AE summaries, and will be included in each of the regimens for which they

were treated and any AEs happening after their last regimen exposure (inclusive of 30 days) will be included in the tally of that regimen.

TEAEs will be summarized by regimen and overall. The tables will include the number and percentage (N [%]) of subjects reporting any event for that term. The denominator, within a regimen summary, will be the total number of subjects that received the regimen.

The following TEAE tables will be summarized by part.

- Overview of TEAEs.
- TEAEs by SOC and PT.
- Most Frequent TEAEs by PT term
- Most Frequent Non-Serious TEAEs by PT
- Relationship of TEAEs to Study Drug by SOC and PT.
- Study Drug-Related TEAEs by SOC and PT.
- Severity of TEAEs by SOC and PT.
- Severity of Drug-Related TEAEs by SOC and PT.

In addition, pretreatment events (PTEs) will be summarized overall by SOC and PT.

For each regimen and overall, subjects reporting more than one occurrence for a term (SOC or PT) being summarized will be counted only once using the most extreme incident (most severe for the severity tables and related for the relationship to study drug tables).

Most frequent TEAEs are those events occurred in at least $\geq 5\%$ (before any rounding) of subjects in a regimen.

Data listings will be provided for all TEAEs, PTEs, TEAEs that led to study discontinuation, TEAEs that led to abnormal liver functions, SAEs, AEs that resulted in death, and AEs occurring more than 30 days after the last dose of study medication.

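### For 11 to 18 of the 30 days after the last dose, Protocol 10.2.2 requires SAE reports only if judged related, while four other passages set no such condition

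*Protocol*

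**What the plan says.** **Collection.** Protocol 10.2.1.1 starts adverse event collection at consent and has it "continue until 14±2 days after Study Exit Visit or the last dose of study medication". It gives two anchors and no 30-day period. Appendix A footnote (m) adds: "The routine collection of AEs will continue through to the follow-up phone call".

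**Reporting to the sponsor.** Protocol 10.2.2 sets no causality condition inside that period: "When an SAE occurs through the AE collection period it should be reported according to the following procedure". Afterwards it does: "Any SAE spontaneously reported to the investigator following the AE collection period should be reported to the sponsor if considered related to study participation". Appendix B item 13 separately obliges the investigator to tell the sponsor of an SAE within a day, with no causality condition and no end date.

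**Database.** Appendix A footnote (d), repeated in SAP Appendix A: "Any AE/SAE spontaneously reported within 30 days postdose will be included within the database as AEs".

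**Analysis.** Protocol 13.1.4 defines a postdose AE as one that occurs after the first dose and "within 30 days after the last dose of study medication is received". SAP 7.11.1 counts an AE or SAE as treatment-emergent if it "started or worsened after first study drug administration and within 14 days (30 days if SAE) of last dose of study drug", and refers to Protocol 10.2.1.1 for this. Neither definition depends on causality. For subjects who complete all four periods, the SAP attributes events after the last dose to the last regimen only up to 14 days. For subjects who do not complete, it uses 30 days.

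**The concern.** The late reporting rule selects on a variable that the SAP tabulates. SAP 7.11.1 plans a table of relationship to study drug and tables of drug-related events. If late related SAEs are sent and late unrelated ones are not, what is missing depends on the classification being reported. That differs from a short window, which loses events regardless of cause.

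Oversight is also at stake. Protocol 10.3.1 makes the sponsor responsible for expedited reporting, with clocks that run from its own awareness. If an event is withheld because the site called it unrelated, the sponsor has no occasion to question that call.

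**Working it through.** The documents give no figure to reproduce here. The check compares time windows and then asks which events the condition touches.

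**Inputs**
- Study exit is Day 4 of Period 4 and dosing is on Day 1 (Protocol 9.3.4 and 6.1), so exit is 4 − 1 = 3 days after the last dose.
- Collection ends 14±2 days after the anchor (Protocol 10.2.1.1).
- The SAP's SAE limit is 30 days after the last dose (SAP 7.11.1).
- There are four doses, 7 days apart (Protocol 6.1), and 72 subjects.

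**Step 1. Length of the conflict.** Gap = 30 − end of collection, in days after the last dose.

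| Anchor | Collection ends | Gap to day 30 |
|---|---|---|
| Last dose | 14 − 2 = 12 to 14 + 2 = 16 | 30 − 16 = 14 to 30 − 12 = 18 |
| Study exit | 3 + 12 = 15 to 3 + 16 = 19 | 30 − 19 = 11 to 30 − 15 = 15 |

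The range over both anchors is 11 to 18 days. The SAP's day formula (onset − last dose + 1 ≤ 14) is written only for 14 days. If the same form were applied to 30, each gap would shorten by one day.

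**Step 2. Share of the window.**
- Of the 30 days after the last dose: 11/30 = 37% to 18/30 = 60%.
- Of the SAP's SAE window, which opens at the first dose: the last dose falls 3 × 7 = 21 days after the first, so the window is about 21 + 30 = 51 days. The share is 11/51 = 22% to 18/51 = 35%.

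**Step 3. Rules in force during the gap.**

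| Passage | What it governs | Causality condition |
|---|---|---|
| Protocol 10.2.2, last sentence | Report to sponsor | Yes |
| Protocol Appendix B item 13 | Report to sponsor | No |
| Protocol Appendix A footnote (d) | Database entry | No |
| Protocol 13.1.4 | Postdose AE definition | No |
| SAP 7.11.1 | Treatment-emergent SAE count | No |

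No passage says which prevails. There is a further overlap: the condition in 10.2.2 works by time of report, the SAP by onset. An SAE that starts inside the collection period but is first reported after it falls under both sentences of 10.2.2, one with the condition and one without.

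**Step 4. Number of events.** The documents give no SAE rate. Assume a risk of 0.5% to 1% per subject over the 30 days after the last dose, spread evenly.
- Expected SAEs in those 30 days: 72 × 0.005 = 0.36 to 72 × 0.01 = 0.72.
- Expected in the gap: 0.36 × 11/30 = 0.13 to 0.72 × 18/30 = 0.43.

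This is an upper bound on what the condition could remove. It includes SAEs judged related, which 10.2.2 does send, and SAEs the site never hears of, which no reporting rule captures.

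**Step 5. Regimen attribution.** In a completer, an SAE on days 15 to 30 after the last dose is treatment-emergent under the SAP but has no stated regimen. Correcting 10.2.2 alone would leave that event without a regimen column.

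**The case against.** The strongest reply is that a late unrelated SAE has other routes to the sponsor. Footnote (d) places it in the database. Protocol 10.2.1.2 puts all AEs on the eCRF whatever the causality opinion, with seriousness recorded, and Protocol 12.1 describes the eCRF as the means of passing study information to the sponsor. Appendix B item 13 asks for notification without qualification. Section 10.2.2 does not require the report, but it does not forbid it either. A reader might infer that such SAEs never reach the sponsor, or that the sponsor cannot review the site's causality call. The documents do not support that. It follows only where a site acts on 10.2.2 alone.

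A reader might also take 37% to 60% as the share of the SAP's SAE window. It is the share of the 30 days after the last dose. The SAP's window opens at the first dose, so 22% to 35% is the right figure.

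The objection adds that related-only reporting after a collection period is a legitimate design choice, and that it causes trouble only because the windows disagree. That is fair, and it is why the remedy has to align the windows as well as reword one sentence. With well under one expected event, there is little distribution to distort in the relationship table.

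What stands is the conflict. 10.2.2 is the section headed for SAE collection and reporting, and for 11 to 18 days it is at odds with four other passages.

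**Conclusion.** The point holds as a conflict between reporting rules. It does not show that events will be lost. For 11 to 18 of the 30 days after the last dose, an SAE that the SAP would count is one that 10.2.2 does not require the site to send if it is judged unrelated. Selective incompleteness of the SAE count and the relationship table is conditional on a site following 10.2.2 by itself.

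The practical size is small. On the assumed 0.5% to 1% risk, 0.13 to 0.43 SAEs fall in the gap, and fewer would be affected. The primary endpoints, Cmax and AUC72, are untouched. The correction is still worth making because it costs almost nothing and, where SAEs are rare, one withheld event could be a large part of the SAE table. The day counts rest on the protocol's own timings. The 51-day window assumes doses exactly 7 days apart, whereas Appendix A footnote (a) allows longer intervals.

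**What to change.** Reconcile the passages to one SAE window and one reporting rule.
- **Protocol 10.2.2:** state that SAEs with onset up to 30 days after the last dose that become known to the investigator are reported within 24 hours regardless of relationship. Apply the related-only condition after that.
- **Protocol 10.2.1.1:** choose one anchor and add the 30-day SAE period, since the SAP cites this section for a window it does not contain.
- **Appendix A footnote (d), in both documents:** cross-refer to the revised 10.2.2.
- **SAP 7.11.1:** for completers, extend last-period regimen attribution from 14 to 30 days for SAEs, and write out the day formula for the 30-day limit.

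The gap between the reporting rule and the SAP's SAE count then falls to 0 days. The cost is a few sentences in a protocol amendment and a SAP update, with perhaps a rare extra SAE form. No visit, call or test is added. Active collection would still end at the follow-up call, so the 30-day figure would cover only SAEs that become known to the site, and the SAP should say so.
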